3.2.6 Concomitant therapy

Concomitant therapies are defined as any medications (excluding study drugs, prior antineoplastic treatments and blood transfusions), surgeries or procedures (including physical therapy) administered in the study and are recorded in the Prior and Concomitant Medications and the Surgical and Medical Procedures eCRF, respectively.

Concomitant medications will be coded using the WHO Drug Reference Listing (WHO DRL) dictionary that employs the WHO ATC classification system. Surgeries or procedures will be coded using the latest MedDRA terminology prior to database lock. All summaries will be tabulated using frequency counts and percentages.

Concomitant therapies will be summarized by ATC class and PT. Surgeries and medical procedures will be summarized by primary system organ class and PT. These summaries will include

- medications/surgeries and medical procedures starting on or after the start of study treatment but starting no later than 30 days after last dose of study treatment, and
- medications/surgeries and medical procedures starting prior to the start of study treatment but continuing after the start of study treatment.

All concomitant therapies and surgeries and medical procedures will be listed. Any concomitant therapies/surgeries and medical procedures starting and ending prior to the start of study treatment or starting more than 30 days after the last date of study treatment will be flagged in the listing.

3.2.7 Antineoplastic therapy after discontinuation of study drug

The FAS will be used for all listings and summaries of antineoplastic therapies initiated after discontinuation of study drug. All summaries will be tabulated using frequency counts and percentages.

Antineoplastic medications initiated after discontinuation of study drug will be summarized and listed by ATC class and PT.

Antineoplastic radiotherapy and surgery information since discontinuation of study treatment will be summarized and listed.

3.2.8 Pharmacokinetic evaluation – primary analysis of the trial

The primary objective is to characterize the PK profile of LDK378 in Chinese adult patients with ALK-rearranged NSCLC previously treated with crizotinib following single and multiple once daily oral doses of LDK378.

Extensive PK assessment consisting of pre-dose trough PK, sparse post-dose PK as well as intensive PK sampling during the 5-day PK run-in period and Cycle 2 Day 1 will be collected in the first 15 enrolled patients to obtain approximately 12 evaluable full PK profiles. Separated from this subset of patients with extensive PK assessment, sparse post-dose PK samples will be collected on Cycle 1 Day 1, Cycle 1 Day 8 and Cycle 2 Day 1, in addition to pre-dose trough PK in the rest of the enrolled patients.

Only PK trough plasma concentrations with non-missing date and time and for which the last prior dose date and time are non-missing will be included in the PK analysis. Unscheduled samples are not included in summary analysis. These samples will be flagged in the corresponding concentration listing.

For patients with extensive PK data, the following PK parameters of LDK378 will be calculated from the individual concentration-time profile obtained from serial PK samples (see [Table 3-1](#)). The non-compartmental method will be used with the aid of using Phoenix WinNonlin (Version 6.2 - Pharsight, Mountain View, CA).

Among the parameters, Cmax, Tmax, AUC0-24h, AUClast and AUCinf are considered as primary; and the following are considered secondary: T1/2, T1/2, acc, Lambda_z, Racc, CL/F (or CLss/F at steady state), Vz/F.

Table 3-2 Noncompartmental pharmacokinetic parameters

Parameter	Descriptor	Primary or Secondary
AUClast	The area under the concentration-time curve from time zero to the last measurable concentration time (ng*h/mL)	Primary
AUC0-24h	The area under the plasma concentration-time curve calculated from time zero to 24 hours (ng*h/mL)	Primary
AUCinf	The area under the plasma concentration- time curve from time zero to infinity (ng*h/mL)	Primary
Cmax	The observed maximum plasma concentration following administration (ng/mL)	Primary
Tmax	The time to reach peak or maximum concentration (h)	Primary
Lambda_z	Terminal elimination rate constant (1/h)	Secondary
T1/2	Elimination half-life determined as $0.693/\lambda_z$ (h)	Secondary
T1/2,acc	The effective half-life determined according to Racc (h)	Secondary
Racc	Accumulation ratio calculated using AUC_{tau} , ss/ AUC_{tau} , sd where tau is the dosing interval	Secondary
CL/F	The total body clearance from plasma (L/h). CL_{ss}/F is calculated from AUC_{tau} assuming steady state ($CL_{\text{ss}}/F = \text{Dose}/AUC_{\text{tau}}$) (L/h)	Secondary
Vz/F	The apparent volume of distribution during the terminal elimination phase (L)	Secondary

Note: the above pharmacokinetic parameter nomenclature follows Novartis internal guidance
[DMPK R0900136]

LDK378 concentrations

Summary statistics, including n, mean, SD, CV for mean, geometric mean, CV for geometric mean, median, minimum and maximum, will be tabulated for concentration versus time profile of LDK378 using PAS. This will be done separately for patients in PK run-in with extensive PK assessment and the rest of the patients with sparse PK sampling. The PK concentration versus time profiles of LDK378 will also be displayed graphically for full PK profile and trough collections.

PK concentration data will be listed using FAS.

LDK378 PK parameters

Primary and secondary PK parameters except Tmax will be summarized using the same reporting approach as for LDK378 concentrations. For Tmax, median, minimum and maximum will be presented.

Using FAS, the PK parameters will be presented in listings.

Trough concentration

Evaluable concentrations at the following time points will be used: pre-dose samples (in either a full profile, or as a single pre-dose collection), 24h on C1D1 (for sparse assessment), and 24h on C2D1 for patients with extensive PK data.

[figure not shown]
The trough concentration obtained throughout the study will be plotted separately for patients in PK run-in with extensive PK assessment and the rest of patients with sparse PK sampling. Only time points with $n \geq 4$ observations will be shown in the figure.

No model based analyses will be conducted.

Average steady state (SS) Ctrough

Steady state trough PK concentration (SS Ctrough) is defined as evaluable trough concentrations at steady state. This means both the 15 patients in PK run-in with extensive PK assessment and the rest of patients with sparse PK sampling will be considered.

Inter/Intra patient variation

The intra-patient and inter-patient variations will be evaluated using data from patients with more than one steady state evaluable trough PK measurements. The intra-patient and inter-patient variations will be estimated using random effects model with patient as random effect.

Handling of concentrations below LLOQ or missing

Concentration values below the lower limit of quantitation (LLOQ) (< 1.0 ng/mL) will be displayed in listings as zero with a footnote to explain and handled as zero in calculations of summary statistics except for geometric means and associated CVs where they will be set to missing. Any missing PK parameter data will not be imputed.

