1.2.1.2.4 Clinical pharmacokinetics

In adult patients with tumors characterized by genetic abnormalities in ALK [REDACTED] and in healthy volunteers [REDACTED], [REDACTED] and [REDACTED], single-dose pharmacokinetics (PK) of LDK378 in humans has the following features: (1) LDK378 was slowly absorbed, with median peak plasma concentration occurring at approximately 4 to 6 h in patients, and approximately 6 to 8 h in healthy subjects. Following Cmax, LDK378 concentrations declined in a mono-exponential manner. The geometric mean apparent terminal half-life ranged from 31 to 41 h across the

[REDACTED]
[REDACTED]
[REDACTED]
[REDACTED]

400 to 750 mg dose groups in patients and 36 to 48 h across the 450 to 750 mg dose groups in healthy subjects. (2) Cmax and AUClast increased dose-proportionally following single oral administration of LDK378 across the 50 to 750 mg dose groups in patients. (3) moderate to high variability in LDK378 PK parameters has been observed in both healthy subjects and patients. Following single oral doses of 450 to 750 mg in healthy subjects when LDK378 was given alone, the inter-subject variability (geometric mean coefficient of variation; CV% range) was 42-74% and 35-72% for AUClast and Cmax, respectively. The corresponding values in patients were 93% and 87% following single oral doses of 50 to 750 mg based on a model developed for dose proportionality analysis.

Multiple-dose PK of LDK378 following repeated daily oral dosing in patients has the following features: (1) following LDK378 750 mg once daily dosing, steady-state was reached by approximately 15 days with a geometric mean accumulation ratio of 6.2 after 3 weeks; (2) LDK378 demonstrated nonlinear PK over time, as indicated by the observed difference in apparent clearance (CL/F) between single-dose (88.5 L/h at 750 mg) and steady-state at Cycle 2 Day 1 (33.2 L/h at 750 mg). As LDK378 is a substrate as well as a time-dependent inhibitor of CYP3A, it is likely that this PK nonlinearity could be attributed to auto-inhibition of LDK378. In contrast with single dose data, Ctrough on Cycle 2 Day 1 after repeated daily dosing increased with dose in a greater than dose-proportional manner.

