- Patient has been previously treated with more than 2 lines of chemotherapy prior to study entry
- No documentation of disease progression at study enrollment
- No measurable lesion from RECIST 1.1 evaluation at baseline per investigator assessment. For analysis by BIRC assessment based on PPS, 'No measurable lesion at baseline' is based on BIRC assessment per RECIST 1.1.
- RECIST lesions previously been irradiated has been chosen as target lesions without a clear progression since irradiation
- Patient has received an ALK inhibitor investigational agent (except Crizotinib) before first dose of study treatment.
- Patient has a history of carcinomatous meningitis
- Patient with symptomatic central nervous system (CNS) metastases neurologically unstable or has required increasing doses of steroids within the 2 weeks prior to study entry.

Pharmacokinetic Analysis Set

The Pharmacokinetic Analysis Set (PAS) consists of all patients who received at least one dose of LDK378 and have at least one evaluable PK sample.

Depending on whether the sample is part of a full profile or a sparse sample, the specific criteria are listed as follows.

A sparse PK sample is considered to be evaluable if:

- The patient takes study drug according to the original assigned dose for at least 5 consecutive days without interruption or dose modification prior to the PK sampling day (except for PK run-in Day 1 for patients with extensive assessment and Cycle 1 Day 1), AND
- On the PK collection day, the patient takes study drug according to the originally assigned dose,
- Vomiting doesn't occur within 6 hours following the last dose intake prior to the PK sample draw, AND
- For the pre-dose sample, draw occurs between 18 to 30 hours after the last dose intake (except for PK run-in Day 1 for patients with extensive assessment and Cycle 1 Day 1), and
- For the pre-dose sample, the draw occurs before the next dose intake, and
- A sample can be considered to be not evaluable as per scientific judgment of the clinical pharmacology expert

An evaluable full PK profile is defined as:

CONFIDENTIAL - For Business Use Only

- The patient takes study drug according to the original assigned dose for at least 5 consecutive days without interruption or dose modification prior to the PK sampling day (except for PK run-in Day 1 for patients with extensive assessment and Cycle 1 Day1), AND
- No vomiting occurs within 6 hours following the last dose intake prior to the PK sample draw, AND

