4.4 PK analyses

The text below gives more detailed instructions and rules needed for programming of the analyses described in [Section 3.2.8](#).

The random effects model with subject as random effect will be used to estimate the intra-patient and inter-patient variation. The following SAS code will be used:

```
PROC MIXED data = pk dataset;  
  CLASS subject;  
  MODEL Log_Ctrough = / ddfm=kr solution;  
  RANDOM subject;  
  Run;  
  /* Log_Ctrough refers to log transformed SS Ctrough concentration */
```

The inter-patient CV% for SS Ctrough will be calculated as:

CV% = sqrt(exp(variance estimate for random patient effect from SS Ctrough model)-1)*100

The intra-patient CV% for SS Ctrough will be calculated as:

CV% = sqrt(exp(residual variance from SS Ctrough model)-1)*100

Additional details for derivation of PK analysis set and parameters:

When deriving the PK analysis set, flags will be generated for evaluable full PK profile and evaluable sparse PK sample, as well as for each individual criterion under evaluable full PK profile and evaluable sparse PK sample (see [Section 3.1.3](#)).

When presenting figures and concentration summaries associated with full PK profile, the flag for evaluable full profile should be used; when presenting sparse PK samples related outputs, the flag for evaluable sparse sample should be used. A patient is evaluable for PK analysis if

he/she has an evaluable full PK flag or an evaluable sparse PK sample flag. In addition, evaluable trough sample flag and evaluable steady state trough sample flag will also be provided for trough samples and steady state trough sample, respectively. The evaluable criteria are the same as that for a sparse sample.

Evaluable full PK profile flag should be applied to run-in patients with extensive PK collection on the PK run-in Day 1 (from 0 hour to 120 hr post-dose sample), and C2D1 (from 0 hr to 24 hr post-dose).

Evaluable sparse PK sample flag should be applied to PK samples collected on:

- C1D8, C1D15, C3D1 to C6D1 for run-in patients
- all PK samples collected as per Table 7-7 in protocol for non run-in patients
- 0 hour pre-dose for PK run-in day 1 and C2D1 for run-in patients
- 120 hr post-dose for PK run-in day 1 and 24 hr post-dose for C2D1 for run-in patients

Evaluable trough sample flag should be applied to trough samples collected on

- all 0 hour pre-dose samples
- 120 hr post-dose in run-in for run-in patients (it is also 0 hr pre-dose on C1D1 for run-in patients)

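### The steady-state Ctrough variability model leaves out patients with exactly one evaluable trough, which needlessly widens the error of the inter-patient CV

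*SAP*

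**What the plan says.** SAP 3.2.8, under inter/intra patient variation, estimates both components "using data from patients with more than one steady state evaluable trough PK measurements", from a random-effects model with patient as the random effect. SAP 4.4 gives the PROC MIXED code on log-transformed Ctrough: the line "MODEL Log_Ctrough = / ddfm=kr solution", followed by a random subject term. The inter-patient CV% comes from the patient variance and the intra-patient CV% from the residual variance. SAP 4.4 neither repeats the restriction nor gives a reason for it.

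Two definitions decide who can enter the model:
- **Evaluability (SAP 3.1.3).** A sample counts only if the patient "takes study drug according to the original assigned dose for at least 5 consecutive days without interruption or dose modification" before the sampling day. There are further conditions on vomiting, on the draw window and on the dose that day. SAP 4.4 extends this to troughs: "The evaluable criteria are the same as that for a sparse sample".
- **Steady state (SAP 3.2.8).** "Steady state trough PK concentration (SS Ctrough) is defined as evaluable trough concentrations at steady state". No visit is named from which steady state counts. Protocol 1.2.1.2.4 reports for an earlier study that "steady-state was reached by approximately 15 days with a geometric mean accumulation ratio of 6.2 after 3 weeks".

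Other uses of these data carry no such minimum. SAP 3.2.2 tabulates demographics by quartile of average steady-state Ctrough in the Pharmacokinetic Analysis Set, which requires one evaluable PK sample.

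**The concern.** A two-value minimum is natural if each patient must supply a within-patient variance. A one-way random-effects model has no such need. It separates the components from the whole data set, and a patient with one value still shows how far patients lie from the common mean. Removing these patients discards valid data on the inter-patient component.

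The patients removed may also differ from the rest. Because a trough must be taken on the original dose, those with exactly one can include patients who changed dose or stopped soon after reaching steady state. If they tend to have high exposure, leaving them out trims the upper tail and makes the inter-patient CV too small. At stake is how well the study describes the spread of steady-state exposure in Chinese patients.

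**Working it through.** The documents give no precision figure for this analysis, so there is none to reproduce. The number of patients with 0, 1 or more troughs and the intra-patient CV are not given either, and are assumed over a range.

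**Inputs from the documents**
- Treated patients: 103 (Protocol, summary of previous amendments).
- Scheduled steady-state troughs: about 6 per patient if counting starts at Cycle 1 Day 15 (that visit, then Day 1 of Cycles 2 to 6). Run-in patients have one more, at 24 h after the Cycle 2 Day 1 dose (Protocol Tables 7-6 and 7-7, SAP 4.4).
- Inter-subject CV after single doses, used only as an anchor: 42–74% (AUClast) and 35–72% (Cmax) in healthy subjects; 93% and 87% in patients (Protocol 1.2.1.2.4).

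**Assumptions**
- Inter-patient CV 42%, 74% or 93%; intra-patient CV 25%, 30% or 50%.
- Of 103 patients, 10–21 have no evaluable steady-state trough, 5–31 have one and 51–88 have two or more, spread evenly over 2 to 6.

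**Precision, worked case (inter-patient CV 74%, intra-patient CV 30%)**

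Log-scale variances are ln(1 + CV²): inter ln(1.5476) = 0.4367, intra ln(1.09) = 0.0862. A patient with n troughs contributes information on the inter-patient variance of

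½ n² / (0.0862 + 0.4367 n)²

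- n = 1: 1.829
- n = 2, 3, 4, 5, 6: 2.172, 2.308, 2.381, 2.426, 2.457 (average 2.349)

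A single-trough patient thus carries 1.829/2.349 = 78% of the information of an average multi-trough patient. With 61 multi-trough patients the total is 143.1. Adding 21 single-trough patients gives 143.1 + 21 × 1.829 = 181.5. The ratio of standard errors is √(181.5/143.1) = 1.126. The full two-parameter calculation gives relative standard errors of 0.192 with the restriction and 0.170 without, which is 12.5% wider.

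**Precision over the range: extra width of the standard error of the inter-patient variance**

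| Inter / intra CV | 5 with one trough | 10 | 21 | 31 |
|---|---|---|---|---|
| 42% / 25% | 1.8% | 4.0% | 10.3% | 17.6% |
| 74% / 30% | 2.2% | 4.8% | 12.5% | 21.2% |
| 93% / 30% | 2.3% | 5.2% | 13.4% | 22.7% |
| 74% / 50% | 1.6% | 3.5% | 9.0% | 15.3% |

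For the intra-patient variance the largest change in any cell is 0.45%.

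**Bias, by simulation** (103 patients, up to 6 troughs, true inter-patient CV 74%, intra-patient 30%, REML fit, 300 trials per setting; the chance of losing evaluability before each visit is logistic in the patient's true exposure)

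| Link of loss to exposure | Mean number with one trough | More than one: mean CV (SD) | At least one: mean CV (SD) |
|---|---|---|---|
| None | 10.8 | 73.4 (8.3) | 73.4 (7.6) |
| None | 16.6 | 74.4 (8.7) | 74.3 (8.1) |
| Slope 0.5 | 11.4 | 71.4 (7.6) | 72.4 (7.1) |
| Slope 0.5 | 16.4 | 70.4 (8.1) | 72.2 (7.8) |
| Slope 1 | 11.9 | 66.1 (7.6) | 68.8 (7.3) |
| Slope 1 | 15.8 | 63.3 (7.5) | 66.7 (7.1) |

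With no link, neither rule is biased and only the spread differs. With a link, the restriction takes off a further 1.0 to 3.4 points. Admitting single-trough patients removes 32% to 50% of the bias: in the last row it falls from 10.7 to 7.3 points, and 3.4/10.7 = 32%. A second simulation (100 patients, true CV 60%, intra-patient 30%, slopes 1 and 2) gave 52.2 against 54.7 and 44.4 against 48.0. There 2.5/7.8 = 32% and 3.6/15.6 = 23% of the bias is removed.

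**The case against.** Several counter-arguments stand and limit the point.

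- **A reader might infer that the model could use every patient.** It could not. Patients with no evaluable steady-state trough stay out under either rule.
- **A reader might infer that this restriction is why early dose-reducers are missing.** The main cause is the evaluability rule in SAP 3.1.3, which removes any trough without five days on the original dose. The two-trough minimum only adds to that.
- **The link between exposure and early loss is assumed.** Samples also drop out for vomiting, draw times, missing times or expert judgement, and treatment can stop for progression. The 58.4% with dose reductions (Protocol 1.2.1.2.1) comes from an earlier study and is not limited to the first weeks. The documents give no counts by reason.
- **A reader might infer that a primary PK result is affected.** SAP 3.2.8 lists the primary and secondary PK parameters, and the Ctrough CV is in neither list. It is descriptive, with no test.

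Three further arguments do not defeat the point. First, concentration CVs are already reported by time point without the restriction, but they mix the two sources of variation. With components of 74% and 30%, the CV at one visit is √(exp(0.4367 + 0.0862) − 1) = 83%, which does not replace a separate inter-patient estimate. Second, using the same patients for both components is a known convention, but it brings no benefit in this model. Third, scheduled PK sampling ends at Cycle 6 Day 1, before the 24-week primary cut-off, so a change now comes after the troughs were collected. That is a fair cost, and keeping the restricted fit as a sensitivity analysis meets it.

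**Conclusion.** The concern holds in a limited form. The restriction discards single-trough patients who carry real information on the inter-patient variance. Its standard error is about 2% to 23% wider over the assumed 5 to 31 such patients among 103, and the intra-patient estimate is essentially unaffected. Where the trial falls in that range cannot be known from the documents, partly because the start of steady state is undefined. If counting began at Cycle 2 Day 1, a run-in patient reaching only that visit could have two troughs and be kept, while a sparse-sampling patient would have one and be dropped.

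The downward bias of about 1 to 3.6 CV points in the simulated settings is conditional on loss of evaluability rising with exposure. Even then, most or at least half of the total bias would remain after the change. The documents do not support a claim that the reported CV is biased. This is a low-priority improvement to a descriptive output.

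**What to change.** In SAP 3.2.8, under inter/intra patient variation, admit all patients with at least one evaluable steady-state trough in place of those with more than one. Report the numbers with 0, 1 and 2 or more such troughs, and name the visits counted as steady state so that these numbers are well defined. Keep the more-than-one subset as a sensitivity analysis for comparability with the primary clinical study report.

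The model code in SAP 4.4 needs no change and no new data are required. As the analysis is descriptive, there is no type I error cost. The downside is that the final inter-patient CV may differ slightly from one already reported; the sensitivity analysis and a line in the SAP's document history would explain the difference. The change does not address the loss of patients through the evaluability rule, so the CV should be described as applying to patients who stayed on the original dose long enough to give an evaluable trough.
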